## Subgroup analysis

Analyses and modelling above will be repeated in the following subgroups:

• Men and women

TM101-A

Protocol Template for a Research Study\_version 15.0CONFIDENTIAL© Copyright: The University of Oxford and Oxford University Hospitals NHS Foundation Trust 2019Page 19 of28

- Age >65 years; >80 years
- Mean SBP before "Time 0" (>160 mm Hg)
- Previous history of myocardial infarction or stroke
- By CCG area
- Users of the system for at least 6months defined as coded data identifying use recorded in the clinical record at both baseline and between months 6-12
- People with baseline blood pressure ≤140/90 compared to those >140/90mmHg
- Deprivation score (High vs Low)
- Ethnicity

Sample size requirements for this study were determined through simulation, as there is little statistical literature for sample size requirements for multilevel modelling. Data was simulated for systolic BP measurements, nested within patients, nested within practices, with the same structure as that detailed in the statistical modelling section. Normal distributions for BP values and variances around patient and practice mean values were assumed (reflecting random intercept terms). A global mean BP of 148 mm Hg was assumed, with practice variation (standard deviation, SD) of 5 mm Hg about this mean. Within a practice, patient variation (SD) was assumed as 17 mm Hg and measurements within a patient were assumed to vary by 10 mm Hg (SD) about the patient mean. The effect of time was assumed to be 0, clinic BP measurements were assumed to be 5 mm Hg higher than home measurements and 25% of patients were expected to take up the Hypertension Plus system.

Assuming an effect size of -3 mm Hg (BP 3 mm Hg lower in patients using the Hypertension Plus system) and a minimum of 4 BP measurements for each patient, 1000 simulated datasets were created and multilevel models as described in the statistical modelling section were fitted to each simulation. This demonstrated that to achieve 90% power at the 5% significance level for the effect of the Hypertension Plus system, 100 patients each drawn from 8 general practices would be required for this study (800 patients in total, 91% power).

When assuming a smaller effect size (-1 mm Hg) or greater variation (practice SD=10 mm Hg, patient SD = 22 mm Hg or measurement SD = 14 mm Hg), the required sample size was 200 patients from 35 practices, 100 patients from 8 practices, 100 patients from 8 practices or 100 patients from 14 practices respectively. Combining all of these conservative assumptions led to a required sample size 300 patients drawn from 42 practices (12600 patients in total, 90% power).

Assuming an average practice size of 8000 people, a 14% prevalence of hypertension, and an uncontrolled hypertension prevalence of 30%, we expect 336 eligible patients per practice. Considering the scenarios above, that study power is more greatly influenced by the number of practices rather than the number of patients, and the possibility of withdrawal of up to 10% of practices. We anticipate that at least forty and up to approximately sixty practices will contribute, hence adequate power for the comparisons should be available.

## 12. Analytical populations

The primary analysis use data from all eligible patients. Analysts will not be blinded to the exposure status. Secondary analysis will be limited to patients in the exposed group who recorded BP measurements through the Hypertension Plus system on more than 3 occasions ("per-protocol" type analysis)

# 12.1. The Level of Statistical Significance

A 5% significance level will be used for all analyses/ tests.

# 12.2. Procedure for Accounting for Missing, Unused, and Spurious Data.

Due to the use of random effects models, missing data is only expected in covariate data. The primary analysis will use multiple imputation by chained equations to impute missing values, including the outcome(s) in the imputation model. Initially 5 imputed datasets will be created and estimates will be combined across imputations using Rubin's rules. Further imputations will be added if the Monte-Carlo error of estimates exceeds 10% of the corresponding standard error. Multiple imputation will only be employed if variables are missing in less than 20% of patients. For larger proportions of missing data, the covariate will be removed from analyses. Sensitivity analyses will be conducted using complete data only.

# 12.3. Potential biases

# (Adapted from Parker et al In Press 2021)

Bias	Issues		Mitigat	tion

(1) Confounding due to non- randomised

	a)	Patients will not be randomised and there is likely to be variation in implementation between practices.	a)	Analysis will take into account area as similar
design	b) c)	Non-participating patients (comparator group) may be systematically different at baseline from those in the telemonitoring group. Practices who take part may be different to those who do not	b) c)	implementation by area Use practices prior to implementation as comparators Within areas
			This is a study s possibi confou taken i	consider ordering effects an observational o there is always the lity of some residual nding that can not be nto account.
(2) Information bias	BP mea differe leading	asured in the clinic and at home may be nt due to white coat and masked effects g to confounding in terms of change in BP .	a)	In a linear mixed model this can be fully adjusted by adding the

The following table summarises key biases and the mitigation we propose.

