#### Service evaluation procedures flow chart

# 8. PRACTICE IDENTIFICATION

# 8.1. Participating practices

We will work with approximately 60 GP practices (approximately 15 practices from each participating CCG) from areas that are taking part in the Omron Hypertension Plus first phase roll out and use a compatible Electronic Health Record (EHR) system. The precise number of practices will depend on the final number of practices in the first wave using an EHR system.

All participating practices must satisfy the following criteria:

- Practice is using (or planning to use) the Hypertension Plus telemonitoring system
- Utilises compatible EHR system
- Data available for the previous 2 years from practice recruitment are available

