## Statistical modelling

Multilevel models and Difference-in-Differences (DiD) analysis will be used to describe changes in outcomes over time (12 months before and after "Time 0") and the effect of the introduction of the Hypertension Plus system. Difference-in-differences (DiD) allows comparison of differences in outcomes, TM101-A

Protocol Template for a Research Study\_version 15.0 CONFIDENTIAL
© Copyright: The University of Oxford and Oxford University Hospitals NHS Foundation Trust 2019 Page 18 of
28

before and after an intervention, between groups. Bias from unobserved fixed variables within each group is automatically accounted for in this type of analysis but bias from variables that affect allocation to the exposed an unexposed group must still be accounted for.

• Primary outcome (SBP) and secondary DBP outcome:

For the primary outcome (SBP) and secondary outcome of DBP, multilevel linear models will be used to model these outcomes over time, including a fixed linear effect for time relative to "Time 0" and random effects for patient and practice level average BP. The models will also include as fixed effects, an indicator for whether each BP was measured in the clinic or at home, an indicator for exposure and, to estimate difference-in-differences, interaction terms between the exposure and time period variable (initial model).

The addition of random effects for patient and practice level trends into the initial model will be considered by comparing models via the likelihood ratio test and Akaike Information Criterion (AIC), with terms retained if model fit is significant improved or the AIC is lower. Covariates will be included as fixed effects without selection once the initial model is finalised. To account for autocorrelation between BP measurements in the same individual, standard errors will be estimated using robust methods and more specifically the Huber-White Sandwich estimator of the variance which can adjust for within-cluster correlation.

The effect of the Hypertension Plus intervention at 6 and 12 months will be estimated by comparing the estimated BP values in the exposed at unexposed groups at these time points, as derived from the models. These estimates, and estimates from the models will be summarised in tables including p-values and 95% confidence intervals.

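### Section 12.3 offers accounting for area as a mitigation for confounding, but the primary model in Section 11.2 has no area term, so area differences in BP change can enter the estimated system effect

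*Protocol*

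**What the plan says.** **Section 12.3, row 1 of the bias table.** The problem listed is the absence of randomisation and variation in implementation between practices. The first mitigation is "Analysis will take into account area as similar". The table's columns have run together in the text, and the cell continues "implementation by area Use practices prior to implementation as comparators Within areas". The same row concedes that some residual confounding may remain.

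**Section 11.2, Statistical modelling (SBP and DBP).** The initial model has:
- a linear effect of time relative to Time 0;
- a clinic/home indicator;
- an exposure indicator;
- "interaction terms between the exposure and time period variable (initial model");
- "random effects for patient and practice level average BP".

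On practice trends, "The addition of random effects for patient and practice level trends into the initial model will be considered", to be kept on a likelihood ratio test or AIC. Then "Covariates will be included as fixed effects without selection once the initial model is finalised". The covariate list includes the Index of Multiple Deprivation but no CCG or other implementation area. BP control follows the same steps. The workload model has period, exposure, their interaction, and patient and practice random effects.

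**Section 11.2, Subgroup analysis.** The analyses are repeated by CCG area, among other subgroups.

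**Section 8.1.** About 60 practices, "approximately 15 practices from each participating CCG".

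**The concern.** A stated mitigation and the model meant to deliver it do not match. Section 11.2 itself says that variables affecting who ends up exposed must still be accounted for, and the protocol makes area a credible one. Under Section 7.2, primary care organisations decide to commission the system and choose the practices. Time 0 follows local start dates, so areas may contribute different calendar windows, and the model has no calendar-time term.

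Practice intercepts remove differences between areas in BP level. They do not remove differences in BP change, and a difference-in-differences estimate is exposed to exactly those. Users are drawn disproportionately from high-uptake areas and non-users from low-uptake areas. If high-uptake areas also improve hypertension care for everyone, the pooled exposure-by-period term takes up part of that improvement.

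**Working it through.** **1. The plan's own power figure.** Section 11.2 states 91% power for -3 mm Hg with 8 practices of 100 patients. The inputs are SD 5 (practice), 17 (patient) and 10 (measurement), 25% uptake (200 users, 600 non-users) and 4 readings per patient. For alpha, "A 5% significance level will be used for all analyses/ tests"; I take it as two-sided. Reading times are not stated.
- Change scores, 2 readings before and 2 after: SE = sqrt(100 × (1/2 + 1/2) × (1/200 + 1/600)) = 0.816. Then 3/0.816 - 1.96 = 1.71, so power is 95.7%.
- Change scores, 1 before and 3 after: SE = sqrt(100 × (1 + 1/3) × (1/200 + 1/600)) = 0.943, so power is 88.9%.
- Generalised least squares with random patient and practice intercepts, reading times spread over ±12 months, a linear time effect and half the readings at home: SE 0.911, power 90.9%.

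The stated figure is reproduced as a within-patient before/after contrast. The described simulation includes no area effect, so it says nothing about this point.

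**2. Bias from area.** Number of CCGs: 60/15 = 4, taken as equal in size. Let u be uptake and c the area-wide BP change in each CCG, with a true system effect of 0. Then

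bias = Σ(u·c)/Σu - Σ((1-u)·c)/Σ(1-u),

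which equals the sum over CCGs of c × (share of users - share of non-users).

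Uptake and change by CCG are **assumptions**. Mean uptake is held at the protocol's 25%. Change runs evenly from 0 to -R and is larger where uptake is higher.

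Worked case, uptake 10/20/30/40%, c = 0/-1/-2/-3:
- users: (0.1×0 + 0.2×(-1) + 0.3×(-2) + 0.4×(-3))/1.0 = -2.00
- non-users: (0.9×0 + 0.8×(-1) + 0.7×(-2) + 0.6×(-3))/3.0 = -1.33
- bias = -0.67 mm Hg

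| Assumed uptake by CCG | Bias as share of R | R = 2 | R = 3 | R = 5 |
|---|---|---|---|---|
| 15/20/30/35% | 16% | -0.31 | -0.47 | -0.78 |
| 10/20/30/40% | 22% | -0.44 | -0.67 | -1.11 |
| 5/15/25/55% | 36% | -0.71 | -1.07 | -1.78 |

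**3. When it vanishes.** Area differences in BP level alone give 0.00. Differences in change with equal uptake give 0.00. Reversing the association reverses the sign.

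**4. What each model does** (expected coefficient; uptake 10-40%; 60 practices of 60 patients unless stated):

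| Model | R = 2 | R = 5 |
|---|---|---|
| Section 11.2 initial model | -0.44 | -1.11 |
| + area main effect | -0.44 | -1.11 |
| + area × period | 0.00 | 0.00 |
| + random practice trends, 60 patients per practice | -0.34 | -0.37 |
| + random practice trends, 300 patients per practice | -0.17 | -0.10 |

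For the last two rows the trend was represented as a practice-specific before/after shift, with SD equal to that of the assumed area changes. They show how far that provision could help. They do not show what a linear trend over 24 months would achieve.

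**5. Precision.** With 60 practices of 60 patients, the SE of the exposure-by-period term goes from 0.385 to 0.399 with area × period terms at uptake 10-40% (0.399/0.385 = 1.04). It becomes 0.391 at 15-35% and 0.427 at 5-55%.

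**The case against.** **The table does not claim that confounding is dealt with.** A reader might infer that it does. The row lists mitigations and concedes residual confounding. That stands. The concession, however, covers confounding that cannot be taken into account, and area can be.

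**Area is not absent from Section 11.2.** The models are repeated by CCG, and a fit within one CCG removes between-CCG confounding from that result. This is a possible reading of the vague wording in row 1. It still leaves the primary estimate unadjusted, and no combined within-area estimate is specified.

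**The bias is conditional.** It would be wrong to say that CCG differences will be counted as a system effect. Uptake and change must both differ by area and be associated, and even then only a fraction is misattributed. The perfect ordering in the illustration favours the concern.

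**Practice trends may rescue the model.** Section 11.2 expects 336 eligible patients per practice, so the 300-patient row is the relevant one. With changes 0/-1/-2/-3 the practice changes have SD sqrt(1.25) = 1.1 mm Hg, against sampling error of about sqrt(100/300) = 0.58, so retention is plausible. This weakens the point for BP without removing it: the trends are not committed to, some bias remains, and the workload model lists none.

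**A SAP may settle it.** Sections 11.1 and 12.4 make a formal SAP optional, and Section 11.2 writes the model and covariates out. The point is a mismatch between two stated sections, so it does not depend on detail being absent.

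**Expressing the bias in standard errors.** A reader might divide the bias by a planning SE and conclude that the estimate would be badly wrong. Such an SE assumes no variation in change between areas, which the bias presupposes, so the ratio is not meaningful.

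**Conclusion.** The mismatch is established from the text and needs no assumption: row 1 of Section 12.3 relies on accounting for area, and the primary model and covariate list in Section 11.2 do not do so. The by-CCG subgroup does not supply an area-adjusted overall estimate.

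Its consequence is conditional. For uptake of 10-40% and area-wide change over a 2-3 mm Hg range, the bias is about -0.4 to -0.7 mm Hg. That is 15% to 22% of the base planning effect (0.44/3 and 0.67/3), or 44% to 67% of the conservative -1 mm Hg effect. These are illustrations, because the protocol gives neither uptake nor BP change by CCG. The true figure may be zero or of opposite sign, and it would be smaller if practice trends are retained. No size has been worked out for BP control, workload or cost, although the same mechanism applies. The point should be corrected; it does not show that the study's result will be wrong.

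**What to change.** In Section 11.2, add CCG and CCG × before/after period as fixed effects to the SBP, DBP and BP-control models, and likewise to the workload model and the cost model in Section 12.5. Users and non-users are then compared within the same area. State that area means CCG, since the exploratory objectives mention both CCG and PCN areas. A CCG main effect alone would satisfy the wording of row 1 but leave the bias unchanged. Point row 1 of Section 12.3 to these terms, and keep the by-CCG subgroup results as descriptive.

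The cost is about three interaction degrees of freedom per model (four CCGs less one), besides the CCG main effects. The SE rises by about 4% in the 10-40% illustration, and by 11% if uptake is as uneven as 5-55% (0.427/0.385 = 1.11). CCG membership is already needed for the subgroup analysis, so no new data are required. The change should be written in before the final analysis: under Section 12 the analysts are not blinded to exposure, and under Section 12.4 later additions would be labelled post hoc.

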# TM101-A

Protocol Template for a Research Study\_version 15.0

© Copyright: The University of Oxford and Oxford University Hospitals NHS Foundation Trust 2019 Page 21 of 28

		intervention/control in the analysis b) BP control rather than BP level in analyses
(3) High variability in the frequency of readings	Home readings can be several times per day or week whereas clinic readings tending to be 1-4x per year. Furthermore, attendance at clinic may be for some other reason meaning those who attend or not are different systematically	
 
a) Primary analysis utilises all available data
 
b) Consider sensitivity analysis using standardisation of readings over time. This means that we take bp values at fixed time points more specifically at 6 and 12 months with value closest to that time point being the one used for the analysis.
 

(4) Contamination of readings	Home readings can be coded as clinic readings. The automated importing of Hypertension Plus readings into the clinical record should avoid this but it is possible that home readings in the comparator group may also be contaminated as may be readings prior to the implementation period.	
 
a) This may be a problem in both groups
 
b) Hypertension Plus readings will be labelled as such
 

(5) Regression to the mean	People chosen on the basis of raised baseline readings are more likely to have subsequently controlled BP	Both intervention and comparison groups will be chosen using same attributes Consideration of need for matching.
(6) Measurement error	Both operator, system and monitor errors are possible	Operator errors may be more likely by patients but evidence of operator bias is more likely for clinicians. Most of these errors will be similar in both groups
(7) End digit preference	People tend to be more likely to record readings ending in zero	
 
a. We will investigate prevalence in both intervention and comparator groups
 
b. Adjusting for the control/intervention group in a mixed model should be
 

		able to take into account for potential differences in the magnitude of digit preference
(8) Withdrawal bias	Patients may not use the Hypertension Plus system consistently.	We will use intention to treat approach so individuals with any Hypertension Plus activity recorded will be assigned to intervention.

# 12.4. Procedures for Reporting any Deviation(s) from the Original Statistical Plan

Prior to the final analysis, we will consider if the analysis as described above is sufficient or whether a statistical analysis plan is appropriate and this will be finalised. Any subsequent changes to the statistical analysis plan will be described in the final report/ paper. Additional analyses conducted will be clearly specified as post-hoc.

# 12.5. Health Economics Analysis

The staff members' (clinical and technical) consultation time recorded on the clinical system setting up and delivering the service will be extracted and used to calculate the implementation costs. Medication quantities will be extracted from the clinical systems in addition. Time spent training and on other activity not recorded in the clinical system will be estimated.

The primary outcome of the health economics analysis will be the costs of NHS hypertension care including medical consultations and medications. The health economics resource use data will be extracted from GP's clinical routine data 12 months before and after the 'time 0'. Standardized unit costs will be obtained and combined with resource use data to calculate health care costs. Following the same analytical principles, summary statistics of health care costs will be presented, and the Difference-in-difference (DiD) modelling will be used to capture the effect of the implementation of Hypertension Plus using both before and after, and between the intervention and the no-intervention groups.

## **13. DATA MANAGEMENT**

The data management aspects of the study are summarised here with details fully described in the Data Management Plan.

Data will be extracted from practice computer systems and secure data transfer and compiled in anonymised form following secure transfer from the practices. In addition, data will be directly downloaded from the Hypertension Plus system with permission of the relevant data controller. Data will be cleaned and compiled to make them comparable within practices.

## TM101-A

## 13.1. Source Data

Source data is what is recorded in the patients' Electronic Health Records and/or the Hypertension Plus system.

## 13.2. Access to Data

Direct access will be granted to authorised representatives from the Sponsor and host institution for monitoring and/or audit of the study to ensure compliance with regulations.

## 13.3. Data Recording and Record Keeping

The participants will be identified by a unique study specific number and/or code in the dataset (SNOMED in the clinical record). The name and any other identifying detail will NOT be included in any study data electronic file.

The principal data source for this study will be anonymised routinely collected primary care data extracted retrospectively from participating general practices. All GP practices in the UK use a computerised medical system to maintain patient medical records. Data are entered into a patient's computerised medical system as coded data or free text. Coded data, anonymised at source, will be extracted from Electronic Health Records by automatic searches. All anonymised data from GP practices and from Omron via the Hypertension Plus system will be encrypted on transit and at rest. Data will be stored within the Department of Primary Care Health Sciences at Oxford University in a locked server facility and in a secure folder accessible only to researchers participating in the study or who have been granted access by the Principal Investigator.

Anonymised study data will be archived for at least five years in accordance with the PC-CTU's Archiving SOPs.

The Research Team has no roles in updating these clinical data recorded by clinicians as part of their consultation and care. The Research Team, however, maintains an auditable trail for all the stages of data processing to ensure the quality of data are not compromised by the processing.

